### **11.0 REGULATORY INSPECTIONS**

The Investigator and/or delegate should contact Abbott immediately upon notification of a governmental agency inspection at the site. A clinical monitor or designee will assist the Investigator and/or delegate in preparing for the audit.

An Investigator who has authority to grant access will permit authorized governmental agency employees, at reasonable times and in reasonable manner, to enter and inspect any establishment where devices are held (including any establishment where devices are used or where records or results are kept).

An Investigator, or any person acting on behalf of such a person with respect to the study, will permit authorized governmental agency employees, at reasonable times and in reasonable manner, to inspect and copy all records relating to the study.

An Investigator will permit authorized governmental agency employees to inspect and copy records that identify subjects, upon notice that governmental agency has reason to suspect that adequate informed consent was not obtained, or that reports required to be submitted by the investigator, to the Sponsor or IRB/EC have not been submitted or are incomplete, inaccurate, false, or misleading.

### **12.0 STATISTICAL CONSIDERATIONS**

### 12.1 Statistical design, hypotheses, method and analytical procedures

This is a prospective, multicenter, and single arm study.

• Analysis for primary endpoint

The primary endpoint is the event rate of MRI scan-related adverse events. The hypothesis is formally expressed as:

H0: MRI scan-related adverse event rate  $\geq 10\%$ 

H1: MRI scan-related adverse event rate < 10%

MRI-scan related adverse event rate will be summarized as the proportion of subjects who have of MRI-scan related events. The primary endpoint will be tested at the 5% significance level. The null hypothesis will be rejected if the 95% UCB for MRI scan-related adverse event rate is less than 0.10. Confidence intervals will be calculated based on the Clopper-Pearson exact method for binomial proportion.

The performance goal of 10% is based on performance goals used by historical MRI safety studies.  $^{14\text{-}17}$ 

• Analysis for secondary endpoint

The success of each of secondary endpoint will be summarized as the number of success and its percentage, together with its 95% confidence interval estimated using Clopper-Pearson exact method for binomial distribution.

### 12.2 Sample size

The sample size estimation is based on the study design, the purpose of the study, and the primary endpoint, namely the MRI scan-related adverse event rate.

The performance goal for MRI scan-related adverse event rate is 10%. Assuming using MRI conditional SCS systems, the MRI scan-related adverse event rate would achieve 1%. A sample size of 46 scans will be able to provide 80% power at one-sided significant level of 5% for this endpoint. Data from only 1 scan per subject will be collected in the study, so a total of 46 subjects will be enrolled and scanned. Assuming the dropout rate between the enrollment and the MRI scanvisit is about 5%, the total expected sample size is 49 (46/0.95). The sample size was calculated using SAS version 9.3.

# 12.3 Pass/fail criteria to be applied to the results of the clinical study

Not applicable

- **12.4 The provision for an interim analysis** Not applicable
- **12.5** Criteria for the termination of the clinical study on statistical grounds Not applicable

## **12.6** Procedures for reporting any deviation(s) from the original statistical plan

Any deviations from the statistical analysis plan will be documented.

### 12.7 The specification of subgroups for analysis

Not applicable

### 12.8 Procedures that take into account all the data

All subjects who have signed an Informed Consent will be considered enrolled in the clinical investigation (refer to Section 4.8.2). However, it is anticipated that there will be subjects who are enrolled in the study but will not be included in the primary endpoint analysis, such as:

- Subjects who are enrolled but do not meet baseline inclusion or meet exclusion criteria before the MRI scan; these are considered as screen failures
- Subjects who are enrolled but do not receive a MRI scan

### 12.9 The treatment of missing, unused or spurious data, including drop-outs and withdrawals

No imputation technique will be used, unless specified in the guidelines of the questionnaire data.

### 12.10 The exclusion of particular information for the testing of the hypothesis

Not applicable

### 12.11 The minimum and maximum number of subjects to be included for each center

This study is expected to enroll 49 subjects who are previously implanted with a Proclaim Elite or Prodigy MRI neurostimulator at up to 30 centers. From a statistical perspective, there is no expectation for heterogeneity across centers, therefore the minimum number of subjects required from enrolling centers is 1 and the maximum number of subjects is 49.

### **13.0 DOCUMENT RETENTION**

The Principal Investigator (PI) will maintain all clinical study documents from prior, during, and (as specified) after the clinical study on file at the site for a minimum of 15 years after the termination of this study, longer as per local laws, or when it is no longer needed to support a marketing application, whichever is later.

The PI must contact the sponsor prior to destroying or archiving off-site any records and reports pertaining to this study to ensure that they no longer need to be retained on-site.

All original subject files must be stored for the longest possible time permitted by the regulations at the hospital, research institute, or practice in question. If archiving can no longer be maintained at the site, the Investigator will notify the sponsor.

All data and documents will be made available on request of the relevant authorities in case of an audit.

The sponsor will archive and retain all essential clinical study documents from prior, during and (as specified) after the clinical study as per requirements.

## 14.0 AMENDMENTS TO CLINICAL INVESTIGATIONAL PLAN

Study related documents such as, the Investigator Brochure (IB), Report of Prior Investigations (RPI), CIP, CRFs, Informed Consent form and other subject information, or other clinical study documents will be amended as needed throughout the clinical study, and a justification statement will be included with each amended section of a document. Proposed amendments to the CIP will be agreed upon between the Sponsor and the coordinating Investigator (if applicable).

The amendments to the CIP and the subject's Informed Consent will be notified to, or approved by, the IRB/EC and regulatory authorities, if required. The version number and date of amendments will be documented.

The amendment will identify the changes made, the reason for the changes, and if it is mandatory or optional to implement the amendment.

Any amendment affecting the subject requires that the subject be informed of the changes and a new consent be signed and dated by the Investigator at the subject's next follow up.

Changes to, or formal clarifications of, the CIP will be documented in writing and provided to the Investigators. This information will be incorporated when an amendment occurs.

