### 4.9 Informed Consent Process

### 4.9.1 General process

The Investigator or his/her authorized designee (if applicable) will conduct the Informed Consent process, as required by applicable regulations and the center's IRB/EC. This process will include a verbal discussion with the subject on all aspects of the clinical investigation that are relevant to the subject's decision to participate, such as details of clinical investigation procedures, anticipated benefits, and potential risks of clinical investigation participation. Subjects must be informed about their right to withdraw from the clinical investigation at any time and for any reason without sanction, penalty or loss of benefits to which the subject is otherwise entitled. Withdrawal from the clinical investigation will not jeopardize their future medical care or relationship with the investigator.

During the discussion, the Principal Investigator or his/her authorized designee will avoid any improper influence on the subject and will respect subject's legal rights. Financial incentives will not be given to the subject. Subjects may be compensated for time and travel directly related to the participation in the clinical investigation. The subject shall be provided with the Informed Consent form written in a language that is understandable to the subject and has been approved by the center's IRB/EC. The subject shall have adequate time to review, ask questions, and consider participation. The Principal Investigator or his/her authorized designee will make efforts to ensure that the subject understands the information provided. If the subject agrees to participate, the Informed Consent form must be signed and dated by the subject and thereafter by the person obtaining the consent prior to any clinical investigation-specific procedures. The signed original will be filed in the subject's hospital or research charts, and a copy will be provided to the subject.

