# **Clinical Investigation Plan**

Failure to obtain informed consent from a subject prior to clinical investigation enrollment should be reported to Sponsor within 5 working days and to the reviewing center's IRB/EC according to the IRB's/ EC's reporting requirements.

If, during the clinical investigation, new information becomes available that can significantly affect a subject's future health and medical care, the Principal Investigator or his/her authorized designee (if applicable) will provide this information to the subject. If relevant, the subject will be asked to confirm their continuing informed consent in writing.

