### 6.6 1-Month follow-up visit

(In clinic, 1 month  $\pm$  10 days since MRI scan)

The following information will be collected at the 1-month follow-up visit:

- Programming functionality
- AE and/or protocol deviation (if applicable)

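### Section 14.0 names only the investigator as signatory for re-consent and places it at the next follow up, which conflicts with Section 4.9.1 and, read literally, can fall after the MRI scan

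*Combined protocol and SAP*

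**What the plan says.** Three places in the combined protocol and SAP govern consent.

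- **Section 14.0 (amendments).** An amendment that touches the subject requires that he or she be told what has changed and that "a new consent be signed and dated by the Investigator at the subject's next follow up". The sentence mentions no subject signature.
- **Section 4.9.1 (initial consent).** The form "must be signed and dated by the subject and thereafter by the person obtaining the consent prior to any clinical investigation-specific procedures". Section 4.8.2 makes the subject's signed and dated form the point of enrollment.
- **Section 4.9.1, closing paragraph (new information).** If "new information becomes available that can significantly affect a subject's future health and medical care", the investigator passes it on. Where this is relevant, "the subject will be asked to confirm their continuing informed consent in writing". No deadline relative to the scan is given.

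On visits, the synopsis and Table 2 in Section 6.2 give the order as enrollment, baseline, MRI scan with pre- and post-scan checks, and a visit at 1 month. Section 4.8 states that some subjects are scanned only for the study, with no medical need.

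**The concern.** The scan is the procedure that carries the risk: Section 3.3 lists electrode heating, induced currents and device damage among its possible effects. If an amendment changes what subjects are told about those risks, the information and the renewed consent are useful to an unscanned subject only before the scan. This matters most for study-only subjects, who could decline without clinical loss.

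A site that followed Section 14.0 to the letter could also be held to have breached Section 4.9.1. Section 15.1 lists failure to secure consent ahead of investigational activity among the possible reasons for early termination.

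Amendments are a realistic prospect. Section 4.4 allows up to 6 years of enrollment, and Appendix B records two numbered amendments in 2019. These changed the population to be scanned, the list of MRI events exempt from reporting, and the consent section.

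**Working it through.** The plan gives no figure to reproduce on this point, so the check sets the passages side by side.

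**1. Who signs.** Section 4.9.1 has the subject sign, then the person obtaining consent. Section 14.0 names the investigator alone. The closing paragraph of Section 4.9.1 does ask for the subject's written confirmation, but only for significant health information and only where relevant. An amendment can affect a subject without meeting that test, so the paragraph does not settle who signs under Section 14.0.

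**2. When, relative to the scan.** The scheduled contacts, with the plan's own labels:

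| Contact | Called follow-up? | Relative to scan |
|---|---|---|
| Enrollment (6.3) | No | Before |
| Baseline (6.4) | No | Before, possibly same day |
| Pre-scan (6.5.1) | No | Before |
| Immediate post-scan (synopsis) | Yes | After |
| 1 month (6.6: "The following information will be collected at the 1-month follow-up visit") | Yes | After |

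For a subject who has consented but not been scanned, the next contact with that label is after the scan. The activity lists for baseline (6.4) and pre-scan (6.5.1) contain no consent step, so they do not prompt re-consent either.

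**3. Whether the interval exists.** No maximum time from consent to scan is stated. Section 12.2 assumes about 5% dropout between enrollment and the scan visit and enrolls 49 to obtain 46, that is 49 − 46 = 3 subjects. The plan therefore treats the interval as real. The figure of 3 does not measure how many subjects would be in the interval when an amendment arrives; the documents give no such number.

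**4. Whether another passage closes the gap.** I found none that requires re-consent before the scan. The new-information paragraph in 4.9.1 is conditional and undated. Section 14.0 sends amendments to the IRB/EC and authorities where required, but that does not fix the time of the subject's signature. Section 15.1 has subjects informed, if appropriate, when the study is suspended or terminated, and an ordinary amendment triggers neither.

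**The case against.** The strongest reply is that the plan as a whole does not set up investigator-only re-consent. Section 4.9.1 requires the subject's signature on the form, Section 4.8.2 ties enrollment to it, and Section 14.0 itself requires that the subject be informed of the changes, possibly earlier than the signature. On this view Section 14.0 is one poorly drafted sentence. That is fair, and it is why the point is put as a conflict between two sections. A conflict still leaves a site without a clear rule, and Section 14.0 is the specific provision for amendments.

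On timing, it can be said that follow up loosely means the next visit of any kind, as in Sections 6.14 and 7.2, where the term is used generically. Re-consent would then fall at baseline or pre-scan. That reading is possible, but it is not written, and the visit schedule does not label those visits that way. A reader might equally infer that re-consent must come a month late. The documents do not support that as the only literal result, because the synopsis also calls the immediate post-scan assessment a follow-up.

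Exposure is also narrow: it needs an amendment that takes effect between consent and scan, and the interval is brief when the visits fall close together. This stands, and it limits the size of the point.

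**Conclusion.** The conflict is real. Sections 14.0 and 4.9.1 differ on who signs and on when, and on the plan's own visit labels the rule in Section 14.0 allows an enrolled but unscanned subject to be scanned before re-consenting. The conclusion rests on reading follow up as the visit schedule uses it. It applies only to subjects between consent and scan when a subject-affecting amendment takes effect, a number that cannot be derived from the documents.

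A reader might go further and infer that scans made under defective re-consent would be lost from the analysis and endanger the primary test. The documents do not support this. Section 12.8 gives eligibility failures found before the scan and unscanned subjects as its examples of exclusion; the list is open, but consent defects are not on it. Section 4.9.1 answers a failure to obtain consent before enrollment with reporting, not removal of data. The synopsis keeps the study open until data from 46 scanned subjects have been collected, so a lost scan could be replaced. There is no shown effect on sample size, power or the primary analysis. The point is one of subject protection and internal consistency, and is worth correcting on that ground alone.

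**What to change.** Reconcile Section 14.0 with Section 4.9.1 and cross-refer to it. Suggested wording: after an amendment affecting the subject, the new consent form is signed and dated by the subject, and then by the person obtaining consent, before any further study procedure including the MRI scan; subjects already scanned re-consent at their next contact.

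This carries the existing rule of Section 4.9.1 over to amendments. It costs one sentence, and a scan may occasionally have to wait for a signature. No endpoint, sample size or analysis changes.

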### **15.0 INVESTIGATION SUSPENSION OR TERMINATION**

### **15.1** Premature termination of the clinical study

The Sponsor reserves the right to stop the study at any stage with appropriate written notice to the Investigator.

Possible reasons for early termination of the study by the sponsor, either at local, national or international level, may include, but are not limited to:

- The device / therapy fails to perform as intended
- Occurrence of USADE which cannot be prevented in future cases
- Sponsor's decision
- Request from regulatory bodies
- Request of Ethics Committee(s)
- Concern for subject safety and welfare
- Failure to secure subject Informed Consent prior to any investigational activity
- Failure to report unanticipated adverse device effects within 72 hours to Abbott and the EC
- Repeated non-compliance with this CIP or the Clinical Trial Agreement
- Inability to successfully implement this CIP
- Violation of the Declaration of Helsinki 2008 (refer to Appendix C)
- Violation of applicable national or local laws and regulations
- Falsification of data, or any other breach of ethics or scientific principles

The study will be terminated according to applicable regulations.

## **Clinical Investigation Plan**

The Investigator may also discontinue participation in the clinical study with appropriate written notice to the Sponsor.

Should either of these events occur, the Investigator will return all documents to the sponsor, provide a written statement as to why the premature termination has taken place, and notify the IRB/EC and/or the Competent Authority (if applicable). Follow-up for all enrolled subjects will be as per routine care.

A Principal Investigator, IRB/EC or regulatory authority may suspend or prematurely terminate participation in a clinical study at the investigational sites for which they are responsible.

If suspicion of an unacceptable risk to subjects arises during the clinical study, or when so instructed by the IRB/EC or regulatory authority, Abbott may suspend the clinical study as appropriate while the risk is assessed. Abbott will terminate the clinical study if an unacceptable risk is confirmed.

Abbott will consider terminating or suspending the participation of a particular investigational site or Investigator in the clinical study if monitoring or auditing identifies serious or repeated deviations on the part of an Investigator.

If suspension or premature termination occurs, the terminating party will justify its decision in writing and promptly inform the other parties with whom they are in direct communication. The Principal Investigator and Abbott will keep each other informed of any communication received from IRB/EC or regulatory authority.

If for any reason Abbott suspends or prematurely terminates the study at an individual investigational site, Abbott will inform the responsible regulatory authority, as appropriate, and ensure that the IRB/EC are notified, either by the Principal Investigator or by Abbott. If the suspension or premature termination was in the interest of safety, Abbott will inform all other Principal Investigators.

If suspension or premature termination occurs, Abbott will remain responsible for providing resources to fulfill the obligations from the CIP and existing agreements for following up the subjects enrolled in the clinical study, and the Principal Investigator or authorized designee will promptly inform the enrolled subjects at his/her investigational site, if appropriate.

When Abbott concludes an analysis of the reasons for the suspension, implements the necessary corrective actions, and decides to lift the temporary suspension, Abbott will inform the Principal Investigators, IRB/EC, or regulatory authority, where appropriate, of the rationale, providing them with the relevant data supporting this decision.

Concurrence will be obtained before the clinical study resumes from the IRB/EC or regulatory authority where appropriate.

If subjects have been informed of the suspension, the Principal Investigator or authorized designee will inform them of the reasons for resumption.

### 15.1.1 Study conclusion

The study will be concluded when:

- All sites are closed AND
- The final report generated by Abbott has been provided to sites or Abbott has provided formal documentation of study closure.

### **16.0 PUBLICATION POLICY**

The results of the clinical study will be submitted, whether positive or negative for publication.

A 'Publication Agreement' will be signed between the Principal Investigator and the Sponsor either as a separate Publication Agreement or within the Clinical Trial Agreement.

For more information on publication guidelines, please refer to the International Committee of Medical Journal Editors (ICMJE) on www.icmje.org.

This study will be posted on ClinicalTrials.gov and results will be posted on ClinicalTrials.gov as required.

### **APPENDIX A: ABBREVIATIONS**

Abbreviation	Term		
ADE	Adverse Device Effect		
AE	Adverse Event		
ASADE	Anticipated Serious Adverse Device Effect		
CA	Competent Authority		
CIP	Clinical Investigational Plan		
CRF	Case Report Form		
DD	Device Deficiency		
DMP	Data Management Plan		
EC	Ethics Committee		
GP	General Practitioner		
IB	Investigator Brochure		
ICMJE	International Committee of Medical Journal Editors		
IFU	Instructions for Use		
IRB	Institutional Review Board		
ISB	Investigator Site Binder		
ISO	International Organization for Standardization		
MP	Monitoring Plan		
NA	Not Applicable		
PI	Principal Investigator		
PMCF	Post Market Clinical Follow Up		
RDC	Remote Data Capture		
SADE	Serious Adverse Device Effect		
SAE	Serious Adverse Event		
SJM	St. Jude Medical		
US	United States		
USADE	Unanticipated Serious Adverse Device Effect		
WMA	World Medical Association		

# **APPENDIX B: CIP REVISION HISTORY**

Revision History				
Amendment	Version	Date	Rationale	Details
Number				
Not	1.0	26 MAY2015	This version of the CIP	NA
Applicable.			was submitted to TUV.	
Internal				
Not	1 1	12 AUG2015	Additional internal	Pottory recharging data added as
Applicable	1.1	13 AU02013	comments.	an option at unscheduled and
Internal				additional surgery visits.
Document.				-MRI Scan Form was removed as
				this is not applicable.
				-Clinical Coordinating
				Investigator signatory has been
				removed since there will not be a
Not	2.0	14 SED 2015	Additional internal	CCI assigned to the study.
Applicable	2.0	14 SEF 2015	comments on spelling	made
Internal			-Data will be collected	References to eCRF and EDC
Document.			via paper CRF	have been removed.
			-Sample Size was	Sample size has been updated.
			recalculated	
Not	3.0	15 JAN2015	Additional internal	Study activities and data points
Applicable			comments on study	have been revised to align with
Internal			activities and data	the objectives and endpoints of
Not	4 0	18 FEB2016	The word	The procedures and tests applied
applicable	1.0	1012010	'interventional' was	in this study would have been
11			replaced by	applied as standard of care for
			'observational'.	subjects that are clinically
				indicated to undergo a MRI scan
				and being followed up.
			Section 0.0 Data	Deference to the EU US Swige
			Management has been	Safe Harbor framework has been
			updated.	removed since it is no longer
			1	valid. Most current verbiage was
				added.
1	D	27 FEB 2019	Enrollment criteria now	Requirement that MRI be
			allow subjects to	conducted as standard of care has
			receive an MRI scan	been removed. Population now
			solely for research	allows MIKI scans as standard of
			enrollment rate	study
	1		emonition fate.	bludy.

SJM-CIP-10056 Page 39 of 49 This confidential document is the property of Abbott and shall not be reproduced, distributed, disclosed or used without the express written consent of Abbott

			Estimated time to enroll patients has been updated from 10 to 6 years.
		This study will support MRI labeling for Proclaim as well as Prodigy devices.	Proclaim Elite devices have been added to the list of devices included in this study and the study title has been updated.
			The inclusion criteria have been updated to clarify which devices are eligible.
		Unification of CIP across study regions.	Additional relevant clarifications have been made throughout the document
		Abbott/St. Jude Medical integration has	Addition of "malignant tumor" as a possible SAE.
		study-related templates/practices.	References to St. Jude Medical have been changed to Abbott where appropriate.
			Table of devices has been expanded with additional details.
			Clarified Abbott post-market surveillance policy regarding device deficiencies.
			A clinical events committee has been added to reduce bias.
			Section 8.2.1 clarifies how the relationship between adverse events and medical devices should be decided.
			Section 5.0 has been split into multiple sub-sections.
			Guidance for SAE reporting has been updated.
		•	

	Data collection has been revised.	Deidentified DICOM image files have been added to data collection at the MRI scan visit. The image tags will serve a source for scan details that are otherwise difficult to capture.
	Clarification.	Background and rationale was expanded with appropriate citations.
		References to neurostimulation systems have been replaced with SCS or device names where appropriate to clarify the scope of this study.
		Added a list of unavoidable MRI events that are not reportable unless condition worsens or duration exceeds expected timeframe.
		Highlighted MRI-related adverse events in the list of reportable events.
		Added citations for 10% safety performance goal.
		Section 9.1 has been added to expand the description of personal information protection.
		Various typos and grammatical errors have been corrected.
		Version identifier has been changed to "D" for consistency with document control processes.
	Notified Body has been updated.	References to TUV have been replaced by BSI after project transfer completed in December 2018.

2	D	25 JUL 2019	US sites are now allowed in the study to increase enrollment and to increase Abbott's ability to evaluate Proclaim devices (more commonly used at US sites).	Section 4.2 now clarifies that the study will be conducted in up to 10 sites in the US, in addition to the approximately 20 sites in Europe. Similarly, Section 12.11 is updated to indicate that subjects will be enrolled at up to 30 centers.
			Enrollment rate was adjusted following the addition of US sites. The estimated time needed to enroll this subject population remains the same in current update (6 years) because enrollment in previous protocol update (March 2019) did not reflect the situation in the field.	Section 4.4 was updated to indicate that, with the addition of US sites, Abbott expects enrollment rate for patients requiring MRIs with an eligible MR conditional device to be no more than 10 subjects per year.
			Reporting subject death to applicable committee according to geographic location.	In case of death, the investigator will need to notify the IRB (for US sites) or EC (for EU sites) per IRB/EC policy. EC has been added to this version of the protocol (Section 8.2.1).
			Update of informed consent language according to the latest Abbott standard and in view of adding US sites to the study.	Informed consent section (Section 4.9.1) has been updated. Special Circumstances for Informed Consent (Section 4.9.1.1) has been updated with US HIPAA compliant statement.
			Device functionality check further specified. Wording added that supplements MRI Procedure Information Manual to allow	Section 6.2 and Section 6.5.1 has been updated to specify that data collection regarding device functionality includes impedance check, performed before the MRI scan. This can only be done when

	impedance check at	the Clinician Programmer (for
	every MRI scan.	Proclaim devices) or Rapid
		Programmer (for Prodigy devices)
		is present. This requirement at
		every MRI scan has been added to
		the section describing the MRI
		Procedure Information Manual
		(Section 5.4).

